#### 9.7.2. Medications that are Substrates or Inhibitors of P-glycoprotein

In vitro data indicate duvelisib is a substrate for P-glycoprotein (P-gp) and may have the potential to inhibit the activity of P-gp. P-gp substrates or inhibitors may be used as medically indicated but with caution.

Appendix 5 provides a list of medications that are substrates or inhibitors of P-gp. Please note that Appendix 5 is not a comprehensive list of all medications which may be substrates of P-gp or may modulate P-gp activity. The Sponsor should be contacted with any questions regarding concomitant use of medications that are thought to modulate P-gp activity.

#### 9.8. Other Concomitant Therapies

Any other medication which is considered necessary for the patient's welfare, and which is not expected to interfere with the evaluation of duvelisib may be given at the discretion of the Investigator.

#### 9.8.1. Photo Safety

Duvelisib was determined to have the potential for phototoxicity in an in vitro phototoxicity assay and in a follow-up in vivo phototoxicity study. Patients should be advised to use appropriate protective measures to minimize exposure to direct sunlight or ultraviolet light sources during the treatment period and for at least 30 days after the last dose of duvelisib.

### 9.9. Blinding and Unblinding

Treatment assignment is not blinded.

# 9.10. Treatment Compliance

The Investigator will dispense the study drug only for use by patients enrolled in the study as described in this protocol. The study drug is not to be used for reasons other than those described in this protocol.

The Investigator or other study staff will supervise study drug given in the clinic and instruct the patient on duvelisib self-administration. Patients will be asked to bring their duvelisib blister cards with them at each visit. Compliance with protocol-defined duvelisib intake will be checked by pill count.

# **10. ADVERSE EVENT MANAGEMENT**

# **10.1.** Definition of an Adverse Event

An AE is defined as any untoward medical occurrence in a patient administered a medicinal product that does not necessarily have a causal relationship with this treatment. An AE can, therefore, be any unfavorable and unintended sign (including an abnormal laboratory finding), symptom, or disease temporally associated with the use of a medicinal (investigational) product, whether or not related to the study (investigational) product. This includes an exacerbation of pre-existing conditions or events, concurrent illnesses, drug interaction, or the significant worsening of the indication under investigation. Anticipated fluctuations of pre-existing conditions, including the disease under study that does not represent a clinically significant exacerbation or worsening, need not be considered AEs.

Symptoms of the disease under study / lack of efficacy / disease progression should not be classified as an AE as long as they are within the normal day-to-day fluctuation or expected progression of the disease.

It is the responsibility of the Investigator to document all AEs that occur during the study. AEs should be reported on the appropriate page of the eCRF.

# **10.2.** Definition of a Serious Adverse Event

An SAE is any untoward medical occurrence at any dose (including after the ICF is signed and prior to dosing) that:

- Results in death
- Is life-threatening (patient is at immediate risk of death from the event as it occurred)
- Requires inpatient hospitalization (formal admission to a hospital for medical reasons) or prolongation of existing hospitalization
- Results in persistent or significant disability/incapacity
- Results in a congenital anomaly/birth defect

Important medical events that may not result in death, are not immediately life-threatening, or do not require hospitalization may be considered SAEs when, based on appropriate medical judgment, they may jeopardize the patient and may require medical or surgical intervention to prevent one of the outcomes listed in this definition. Examples of such events include allergic bronchospasm requiring intensive treatment in an emergency room or at home, blood dyscrasias or convulsions that do not result in inpatient hospitalization, or the development of drug dependency or drug abuse.

For SAE reporting purposes, hospitalization is defined as an inpatient hospital stay  $\geq$  24 hours. Hospitalizations for elective surgery or other medical procedures that are not related to a TEAE are not considered SAEs. Hospitalization, which in the opinion of the Investigator, is unrelated to the study drug, and due to purely non-medical circumstances (e.g., respite care, lack of a caretaker at home, lack of transportation home) are also not considered to be SAEs. PD under study (including signs and symptoms of progression) if documented by use of appropriate methods, should not be reported as an SAE unless the outcome is fatal during the study or within the safety reporting period (see Section 10.3, Reporting of Adverse Events and Serious Adverse Events). If the malignancy has a fatal outcome during the study or within the safety reporting period, then the event should be reported using the term "disease progression" with a CTCAE severity of Grade 5.

Death is an outcome. The primary reason for patients' death should be reported as an SAE.

# **10.3.** Reporting of Adverse Events and Serious Adverse Events

The AE reporting period begins from the time that the patient signs the ICF through and including 30 calendar days after the last study drug dose. All treatment-related AEs/SAEs should be followed until resolution or stabilization. Any SAE occurring after the reporting period must be promptly reported if a causal relationship to the investigational drug is suspected. If the patient begins a new anticancer therapy, the safety reporting period ends at the time the new treatment is started, however, death must always be reported if it occurs during the AE reporting period irrespective of intervening treatment.

Elective or previously scheduled hospitalizations for pre-existing conditions that have not worsened after initiation of treatment should not be classified as SAEs. For example, an admission for a previously scheduled ventral hernia repair would not be classified as an SAE.

All AEs should be recorded individually unless, in the opinion of the Investigator or designated physician, the AEs constitute components of a recognized condition, disease, or syndrome. In the latter case, the condition, disease, or syndrome should be reported rather than each individual sign or symptom. If a constellation of signs and/or symptoms cannot be medically characterized as a single diagnosis or syndrome at the time of reporting, each individual event should be recorded as an AE or SAE as appropriate on the relevant form(s) (SAE Report Form and/or AE eCRF). If a diagnosis is subsequently established, it should be reported as follow-up information is available. If a diagnosis is determined subsequent to the reporting of the constellation of symptoms, the signs/symptoms should be updated to reflect the diagnosis.

Each AE is to be evaluated for duration, severity, seriousness, and causal relationship to the investigational drug. The action taken with study drug and the outcome must also be recorded.

All SAEs, regardless of relationship to the study treatment, must be reported immediately to the Sponsor and Contract Research Organization (CRO) pharmacovigilance group, with the timeframe not to exceed 24 hours of the Investigator becoming aware of the event. Initial SAE

notification should be made by e-mailing or faxing the SAE report form to the e-mail or fax number provided on the SAE report form.

An initial SAE Report may be sent without the Investigator's signature but must be followed by a report signed by the Investigator within 48 hours of becoming aware of the event. Follow-up SAE reports must be submitted by the Investigator as new information becomes available.

The Medical Monitors for this study may be contacted in case of need for advice or assistance. Contact details will be provided in the Study Manual.

# **10.4.** Severity of Adverse Events

The severity of the AE will be graded according to the NCI CTCAE, version 5.0 (see web page at http://ctep.cancer.gov for details). AEs not listed in the CTCAE should be graded as summarized in Table 11.

CTC Grade	Equivalent To:	Definition
Grade 1	Mild	Discomfort noticed but no disruption of normal daily activity
Grade 2	Moderate	Discomfort sufficient to reduce or affect daily activity; no treatment or medical intervention is indicated although this could improve the overall well-being or symptoms of the patient
Grade 3	Severe	Inability to work or perform normal daily activity; treatment or medical intervention is indicated in order to improve the overall well-being or symptoms; delaying the onset of treatment is not putting the survival of the patient at direct risk
Grade 4	Life-threatening/ disabling	An immediate threat to life or leading to a permanent mental or physical conditions that prevents work or performing normal daily activities; treatment or medical intervention is required in order to maintain survival
Grade 5	Death	AE resulting in death

Table 11:	CTCAE Grading
	CICIL Oraung
# 10.5. Relationship of Adverse Events to Study Drug

The Investigator will make a judgment regarding whether or not the AE was related to study drug, as outlined below:

- **Definitely related**: This category applies when, after careful medical consideration, there is almost no consideration of other causation.
- **Probably related**: There is a clinically plausible time sequence between onset of the AE and study drug administration. The AE is unlikely to be caused by a concurrent or underlying illness, other drugs, or procedures. If applicable, the AE follows a clinically consistent resolution pattern upon withdrawal of study drug.
- **Possibly related**: There is a clinically plausible time sequence between onset of the AE and study drug administration, but the AE could also have been caused by the concurrent or underlying illness, other drugs, or procedures. Information regarding study drug withdrawal may be lacking or unclear. "Possible" should be used when study drug administration is one of several biologically plausible causes of the AE.
- **Unlikely related**: The AE is most likely due to a cause not related to study drug administration. However, association with the study drug cannot be completely ruled out.
- Unrelated: Another cause of the AE is most plausible and a clinically plausible temporal sequence is inconsistent with the onset of the AE and study drug administration and/or a causal relationship is considered biologically implausible.

For the purpose of regulatory reporting requirements, causal relationships of definite, probable, and possible will be considered treatment-related, while unlikely and unrelated will be considered not treatment-related.

# **10.6.** Clinical Laboratory Adverse Events

A clinical laboratory AE is any laboratory value that is deemed clinically significant by the Investigator, is greater than Grade 2 in severity, and is accompanied by one of the following:

- requires a medical intervention
- requires a change or suspension of study drug
- is accompanied by clinical symptoms

Laboratory abnormalities that have not required medical intervention should not be recorded as AEs and will be captured and reported in the Laboratory section of the clinical study report. If a medical intervention occurs, it should be recorded as a treatment with the abnormal laboratory finding as the AE (e.g., anemia with treatment required and blood transfusion recorded as a

procedure, hyperglycemia with treatment required and change in insulin dose recorded on concomitant medications).

The Investigator should decide, based upon the AE criteria and the clinical condition of the patient, whether a change in a laboratory parameter is clinically significant and therefore represents an AE.

If, at the end of the treatment phase with the study drug, there are pathological laboratory values which were not present at Baseline, further clinical or laboratory investigations should be performed until the values return to within reference range or until a plausible explanation (i.e., concomitant disease) is found for the pathological laboratory values.

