#### Table 8: Duvelisib Dose Modification and Toxicity Management

Treatment Related Toxicity 	Adverse Reaction Grade	Duvelisib Dose Modification and Toxicity Management
	Grade 1-2	
 
No change in dose
 
Initiate supportive care with emollients, anti- histamines (for pruritus), or topical steroids
 
Monitor closely
 

Cutaneous reactions	Grade 3	
 
Withhold until resolved
 
Initiate supportive care with emollients, antihistamines (for pruritus), or topical steroids
 
Monitor at least weekly until resolved
 
Resume at reduced dose (see Table 9)
 
If severe cutaneous reaction does not improve, worsens, or recurs, discontinue
 

	Life-threatening	• Discontinue
	SJS, TEN, DRESS (any grade)	• Discontinue
Pneumonitis without suspected infectious cause	Moderate (Grade 2) symptomatic pneumonitis	
 
Withhold
 
Treat with systemic steroid therapy
 
If pneumonitis recovers to Grade 0 or 1, duvelisib may be resumed at reduced dose (see Table 9)
 
If non-infectious pneumonitis recurs or patient does not respond to steroid therapy, discontinue
 

	Severe (Grade 3) or life- threatening pneumonitis	

Discontinue

Treat with systemic steroid therapy

	3 to 5 × upper limit of normal (ULN) (Grade 2)	
 
Maintain duvelisib dose
 
Monitor at least weekly until return to < 3 × ULN
 

ALT/AST elevation	> 5 to 20 × ULN (Grade 3)	
 
Withhold duvelisib and monitor at least weekly until return to < 3 × ULN
 
Resume duvelisib at same dose (first occurrence) or at a reduced dose for subsequent occurrence (see Table 9)
 

	> 20 × ULN (Grade 4)	Discontinue duvelisib
Hematologic Adverse	Reactions	
Febrile neutropenia	Grade 3-4	
 
Withhold duvelisib until afebrile and resolution of Grade 3 or Grade 4 neutropenia to Grade ≤ 2 (ANC > 1.0 Gi/L)
 
Monitor ANC at least weekly until > 1.0 Gi/L
 
Resume at same dose (first occurrence) or at a reduced dose for subsequent occurrence
 

Treatment Related Toxicity 	Adverse Reaction Grade	Duvelisib Dose Modification and Toxicity Management
	Absolute neutrophil count (ANC) 0.5 to 1.0 Gi/L	

Maintain duvelisib dose

Monitor ANC at least weekly

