Neutropenia	ANC less than 0.5 Gi/L	
 
Withhold duvelisib
 
Monitor ANC until > 0.5 Gi/L
 
Resume at same dose (first occurrence) or at a reduced dose for subsequent occurrence (see Table 9)
 

	Platelet count 25 to < 50 Gi/L (Grade 3) with Grade 1 bleeding	

No change in dose

Monitor platelet counts at least weekly

Thrombocytopenia	Platelet count 25 to < 50 Gi/L (Grade 3) with Grade 2 bleeding or Platelet count < 25 Gi/L (Grade 4)	
 
Withhold duvelisib
 
Monitor platelet counts until ≥ 25 Gi/L and resolution of bleeding (if applicable)
 
Resume at same dose (first occurrence) or resume at a reduced dose for subsequent occurrence (see Table 9)
 

Abbreviations: ALT = alanine aminotransferase; ANC = absolute neutrophil count; AST = aspartateaminotransferase; CMV = cytomegalovirus; DRESS = drug reaction with eosinophilia and systemic systems; Gi =1 x 10^9; PCR = polymerase chain reaction; PJP =*Pneumocystis jirovecii;*pneumonia; SJS = Stevens-Johnsonsyndrome; TEN = toxic epidermal necrolysis; ULN = upper limit of normal

1. Treatment-related toxicity: possible, probable, or definite relationship to study treatment

2. Toxicity grades are defined per CTCAE version 5.0. Note if parameter is not defined by CTCAE, then AE grading criteria (Section 10.4) should be utilized.

Duvelisib may be held up to 42 days for toxicity. Doses held for > 42 days due to treatmentrelated toxicity will result in permanent discontinuation from duvelisib unless Sponsor Medical Monitor approves resuming treatment after Investigator confirmation of acceptable benefit-risk assessment. Any patient who requires a dose-level reduction to below dose level -3 (see Table 9) due to treatment-related toxicities will be permanently discontinued from duvelisib treatment.

In the event that study drug is discontinued due to any reason other than PD (e.g., AE), patients should continue disease response assessments until documentation of PD, as determined by the Investigator, death, or new anticancer treatment as outlined in Table 3 or Table 5.

Dose reduction levels, based on the patient's initial assigned dose optimization dose level, are shown in Table 9.

Table 9:	Duvelisib	Dose Reduction	Levels for	Patients F	Receiving	25 mg	g or 75 mg	g BID
						c		7

Dose Level	Duvelis	ib (mg)
Starting Dose	25 BID	75 BID

-1	15 BID	50 BID
-2	10 BID	25 BID
-3	5 BID	15 BID

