5.3.1.1 Other Adverse Events of Interest

Selected MedDRA PTs will be combined to create grouped PTs or categories to further characterize risks associated with duvelisib. The following risks will be summarized:

Grouped Term	Preferred Terms
Diarrhea	Diarrhoea, Diarrhoea hemorrhagic, Defecation urgency
Colitis	Colitis, Colitis erosive, Enterocolitis, Enterocolitis hemorrhagic, Colitis microscopic, Necrotising colitis, Colitis ulcerative
Pneumonia	Pneumonia, any PT containing the word/string "pneumonia" except for "Pneumonia aspiration", Atypical pneumonia, Atypical mycobacterial pneumonia, Bronchopneumonia, Bronchopulmonary aspergillosis
Pneumonitis	Pneumonitis, Interstitial lung disease, lung infiltration, acute interstitial pneumonitis
Transaminase elevation	Alanine aminotransferase increased, Aspartate aminotransferase increased, Transaminases increased, Hypertransaminasaemia, Hepatic enzyme increased, Acute hepatic failure, Drug-induced liver injury, Hepatic failure, Hepatocellular injury, Hepatotoxicity
Cutaneous reactions	Dermatitis, Dermatitis allergic, Dermatitis bullous, Dermatitis exfoliative, Dermatitis psoriasiform, Drug eruption, Drug reaction with eosinophilia and systemic symptoms, Erythema, Erythema multiforme, Generalised erythema, Exfoliative rash, Rash, Rash generalised, Rash erythematous, Rash follicular, Rash macular, Rash maculo-papular, Rash maculovesicular, Rash papular, Rash papulosquamous, Rash pruritic, Rash pustular, Rash vesicular, Toxic skin eruption, Palmar erythema, Palmoplantar keratoderma, Palmar-plantar erythrodysesthesia syndrome, Perivascular dermatitis, Skin reaction, skin toxicity, Stevens-Johnson syndrome, Toxic epidermal necrolysis
Neutropenia	Neutropenia, Neutrophil count decreased

The specific PTs that will be combined for each risk will be defined in the analysis dataset programming specifications.

For each risk, PTs will be summarized at the grouped PT and individual PT (and grouped SOC if applicable), at the patient level:

- TEAEs (All Grades, All Causalities)
- Treatment-related TEAEs (All Grades)
- Grade 1 or 2 only TEAEs (All Causalities)

- Grade 3 or higher TEAEs (All Causalities)
- Grade 4 TEAEs (All Causalities)
- TEAEs resulting in death (All Causalities)
- Treatment-emergent SAEs (All Causalities)
- Treatment-related treatment-emergent SAEs
- TEAEs resulting in dose hold (overall and by resolution)
- TEAEs resulting in dose reductions (overall and by resolution)

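### Protocol 10.6 gives opposite instructions on recording a Grade 3 or higher laboratory abnormality that led only to a drug hold or only to symptoms, so transaminase and severe neutropenia TEAEs may be under-counted and recorded inconsistently

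*Protocol*

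**What the plan says.** Protocol 10.6 (Clinical Laboratory Adverse Events) opens with a definition. A laboratory AE is a value that the investigator deems clinically significant, that "is greater than Grade 2 in severity, and is accompanied by one of the following": a need for medical intervention, a study drug consequence ("requires a change or suspension of study drug"), or clinical symptoms. One of the three is enough.

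The next paragraph begins: "Laboratory abnormalities that have not required medical intervention should not be recorded as AEs". It adds that such abnormalities will instead appear in the laboratory section of the study report. It continues: "If a medical intervention occurs, it should be recorded as a treatment with the abnormal laboratory finding as the AE", with a transfusion for anemia and an insulin change for hyperglycemia as examples. A later paragraph leaves it to the investigator to decide, using the AE criteria and the patient's condition, "whether a change in a laboratory parameter is clinically significant and therefore represents an AE".

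Protocol Table 8 sets the response to abnormal values. For Grade 3 ALT/AST elevation it reads "Withhold duvelisib and monitor at least weekly until return to" below 3 × ULN. The row for "ANC less than 0.5 Gi/L" likewise calls for withholding and monitoring. Neither row names any other treatment.

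TEAEs and changes in laboratory values together form a secondary endpoint (Protocol 3.1.2 and 3.2.2). SAP 5.3.1.1 tabulates recorded TEAEs for grouped risks, including transaminase elevation and neutropenia. Its tables cover treatment-related events, dose holds, reductions, discontinuations, time to onset and duration.

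**The concern.** Two instructions in adjacent paragraphs disagree about the same patient. If a Grade 3 ALT leads to a drug hold and nothing else, a coordinator who stops at the three-condition list enters an AE. One who reads on to the next paragraph does not. Table 8 makes that pattern foreseeable for two of the risks that Protocol 1.4 names as important and identified.

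Causality and action taken with study drug are recorded for each AE (Protocol 10.3). An event that is never entered as an AE therefore has neither, and it cannot appear in any table that needs them. The Expansion Phase runs at approximately 40-50 centers, so incidence in those tables could depend partly on which paragraph each site followed. A hold could also appear in the exposure summaries with no AE behind it.

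**Working it through.** There is no figure in the plan to reproduce on this point. The check is a comparison of texts, followed by a short illustration of scale.

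**1. The two instructions, case by case.** Take a value above Grade 2 that the investigator judges clinically significant.

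| What accompanied the value | Three-condition list | Sentence that follows | Result |
|---|---|---|---|
| Medical intervention | AE | Not excluded | Agree: AE |
| Drug hold or dose change only | AE | Not an AE | Conflict |
| Symptoms only | AE | Not an AE | Conflict |
| None of these | Not an AE | Not an AE | Agree: not an AE |

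**2. Could a hold count as a medical intervention?** That reading would remove the conflict for holds, but the text does not allow it. The list gives intervention and study drug change as separate conditions, and the examples of intervention are a transfusion and an insulin change. Symptoms alone are not an intervention on any reading.

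**3. Does investigator judgment settle it?** No. The judgment is to be made by reference to the AE criteria, and those are the instructions in conflict.

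**4. Where hold-only cases arise.**
- Grade 3 ALT/AST (above 5 to 20 × ULN): withhold and monitor. In conflict.
- ANC below 0.5 Gi/L: withhold and monitor. In conflict if nothing else is given. If growth factor is given, which Protocol 9.5.2 permits, that is an intervention and both instructions lead to an AE.
- ANC 0.5 to 1.0 Gi/L: dose maintained. Without symptoms or intervention, both instructions agree that there is no AE.

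The neutropenia part of the point is therefore mainly about untreated ANC below 0.5 Gi/L.

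**5. What is lost and what survives if a site follows the second instruction.**
- Lost: the event's contribution to the TEAE tables of SAP 5.3.1 and 5.3.1.1, including treatment-related events, those leading to hold, reduction or discontinuation, onset and duration.
- Kept: worst post-baseline CTCAE grade and shift from baseline, by Grade 1-2, 3-4, 3 and 4, plus a listing of Grade 3 or 4 values (SAP 5.3.2).
- Kept: numbers of patients with a hold, a reduction or discontinuation of drug (SAP 5.1.7).

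**6. Scale, as illustration only.** Let h be the share of Grade 3 or higher events that are managed without intervention and also left unrecorded. Then

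recorded rate = true rate × (1 − h).

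The documents do not give h. For a reference rate, Protocol 1.2 reports Grade 3 or higher events in a combined Phase 1 group of 35 patients with peripheral or cutaneous T-cell lymphoma: transaminase elevation 11/35 = 31.4%, neutropenia 3/35 = 8.6%.

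| Assumed h | Transaminase recorded | Neutropenia recorded |
|---|---|---|
| 0 | 31.4% | 8.6% |
| 0.5 | 15.7% | 4.3% |
| 1 | 0% | 0% |

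The table shows direction only: relative to the list, the recorded rate falls or stays the same.

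**The case against.** The best case for the plan is that other text favors recording. Protocol 9.4.2 applies Table 8 when a patient has an AE at least possibly related to duvelisib, so a hold made under that table presupposes an AE. The general definition in Protocol 10.1 includes abnormal laboratory findings and asks investigators to document all AEs. Neutropenia was evidently recorded as an AE in the Dose Optimization Phase (Protocol 1.3). The laboratory half of the secondary endpoint is reported regardless of AE entry. All of this stands, and it limits the point. It does not remove it: none of these passages says which paragraph of 10.6 governs, and the presence of neutropenia AEs does not show that recording was complete.

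Three stronger readings are tempting and should not be drawn:
- *That these TEAEs will be under-counted.* The count falls only where a site followed the second instruction, and the documents do not show that any did.
- *That about 31 Grade 3 or higher transaminase events per 100 patients could shrink to almost none.* That is 0 to 100% of a borrowed rate. The low end requires nearly every event to be hold-only and nearly every site to leave it out. The rate also comes from a mixed Phase 1 group, not from the Expansion regimen.
- *That the SAP contradicts 10.6 by tabulating TEAEs of Grade 1 or 2 only.* That row belongs to a template applied to every risk group, and the transaminase group also contains terms that are not laboratory values, such as hepatotoxicity. Low-grade laboratory incidence is given in SAP 5.3.2. A sparse row is not an error.

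**Conclusion.** Protocol 10.6 is wrong as written: it gives opposite instructions for a clinically significant value above Grade 2 that led only to a drug hold or dose change, or only to symptoms. Because Table 8 produces hold-only cases for Grade 3 ALT/AST and for ANC below 0.5 Gi/L, transaminase and severe neutropenia TEAEs may be under-counted and recorded inconsistently across sites.

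The direction, relative to the three-condition list, is downward or nil. The size cannot be derived, because neither the hold-only share nor site practice is in the documents. The exposure is confined to AE-linked tables. ORR by IRC and the sample size are not affected. The conclusion rests on reading a drug hold as distinct from a medical intervention, which the section's own list and examples support.

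**What to change.** 1. Reconcile the two passages of Protocol 10.6 so that only laboratory abnormalities meeting none of the three listed conditions are left unrecorded as AEs. This is a change of one sentence. It alters no dosing or toxicity management rule.
2. Before database lock, match Grade 3-4 laboratory values (the SAP 5.3.2 listing) that coincide with a hold or dose change (the SAP 5.1.7 dose modification listing) against the AE dataset, and query those without a corresponding AE. The reworded sentence acts only on later entries; this check covers records already made.

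The cost is some data queries, and reported TEAE rates may rise. Rebuilding the SAP 5.3.1.1 tables from laboratory data would be a matter of preference and is not needed to cure the contradiction.
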